## **6.8. Long-Term Follow-up**

Long-term follow-up (LTFU) for overall survival begins after the EOS visit, or the last visit on study if EOS does not occur. Subjects will be contacted via phone call every 3 months for determination of long term survival status and record of any other anti-cancer therapy, cancer related surgery for up to 5 years after the EOS visit.

Subjects who are not deceased by the time Gilead has made the determination the study will be ended will receive a final follow-up phone call to assess survival status and communicate the Sponsor's decision.

The investigator will make every effort to contact the subject or a close relative or caretaker by phone to collect survival information. The investigator should show due diligence by documenting in the source documents steps taken to contact the subject (ie, dates of phone calls, registered letters, etc).

See Section 3.7 for reasons for discontinuing long-term follow-up and study completion.

## **6.9. Unscheduled visits**

Unscheduled visits may occur at any time while the subject is enrolled on study. Vital signs, laboratory assessments, ECG, and physical examination may be conducted at these visits. Data generated during an unscheduled visit will be collected on the eCRF.

## **6.10. Protocol Deviations**

Gilead's policy prohibits exemptions from protocol inclusion/exclusion criteria. In the event of a significant deviation related to gross non-compliance from the protocol or incidences that impose significant risk to subject safety, the investigator or designee must notify Gilead and/or its designee immediately. The site will be required to document deviations in accordance with Gilead's procedures and in accordance with the site's procedures and processes.

## **7. ADVERSE EVENTS AND TOXICITY MANAGEMENT**

### **7.1. Definitions of Adverse Events, Adverse Reactions, and Serious Adverse Events**

#### **7.1.1. Adverse Events**

An AE is any untoward medical occurrence in a clinical study subject administered a medicinal product, which does not necessarily have a causal relationship with the treatment. An AE can therefore be any unfavorable and/or unintended sign, symptom, or disease temporally associated with the use of a medicinal product, whether or not considered related to the medicinal product. AEs may also include pre- or post-treatment complications that occur as a result of protocol specified procedures, lack of efficacy, overdose, drug abuse/misuse reports, or occupational exposure. Preexisting events that increase in severity or change in nature during or as a consequence of participation in the clinical study will also be considered AEs.

An AE does not include the following:

- Medical or surgical procedures such as surgery, endoscopy, tooth extraction, and transfusion. The condition that led to the procedure may be an adverse event and must be reported.
- Pre-existing diseases, conditions, or laboratory abnormalities present or detected before the screening visit that do not worsen
- Situations where an untoward medical occurrence has not occurred (eg, hospitalization for chemotherapy infusion per institutional guidelines, elective surgery, social and/or convenience admissions)
- Overdose without clinical sequelae
- Any medical condition or clinically significant laboratory abnormality with an onset date before the consent form is signed and not related to a protocol-associated procedure is not an AE. It is considered to be pre-existing and should be documented on the medical history eCRF.

#### **7.1.2. Serious Adverse Events**

An SAE is defined as an event that, at any dose, results in the following:

- Death
- Life-threatening (Note: The term “life-threatening” in the definition of “serious” refers to an event in which the subject was at risk of death at the time of the event; it does not refer to an event that hypothetically might have caused death if it were more severe.)

- In-patient hospitalization or prolongation of existing hospitalization (Note: Hospitalization for chemotherapy infusion per institutional guidelines will not be considered an SAE.)
- Persistent or significant disability/incapacity
- A congenital anomaly/birth defect
- A medically important event or reaction: such events may not be immediately life-threatening or result in death or hospitalization but may jeopardize the subject or may require intervention to prevent one of the other outcomes constituting SAEs. Medical and scientific judgment must be exercised to determine whether such an event is a reportable under expedited reporting rules. Examples of medically important events include intensive treatment in an emergency room or at home for allergic bronchospasm; blood dyscrasias or convulsions that do not result in hospitalization; and development of drug dependency or drug abuse. For the avoidance of doubt, infections resulting from contaminated medicinal product will be considered a medically important event and subject to expedited reporting requirements.

#### 7.1.2.1. Protocol-Specific Serious Adverse Event Instructions

To maintain the integrity of the study, disease progression and death from disease progression should be reported as SAEs by the investigator only if it is assessed that the study drugs caused or contributed to the disease progression (ie, by a means other than lack of effect). Unrelated disease progression should be captured on the eCRF.

In addition, events that are indicative of the following disease-related SAEs that are assessed as unrelated to study drugs will not be reported as expedited reports by Gilead during the study:

- Progression of gastric cancer
- Death related to disease progression

These events will be exempt from global expedited reporting requirements for the duration of the study as they are the primary endpoints of this study. They will be reported as appropriate in the final clinical study report as well as any relevant aggregate safety report.

#### 7.2. Assessment of Adverse Events and Serious Adverse Events

The investigator or qualified subinvestigator is responsible for assessing AEs and SAEs for causality and severity, and for final review and confirmation of accuracy of event information and assessments.

### **7.2.1. Assessment of Causality for Study Drugs and Procedures**

The investigator or qualified subinvestigator is responsible for assessing the relationship to IMP therapy using clinical judgment and the following considerations:

- **No:** Evidence exists that the adverse event has an etiology other than the study drug. For SAEs, an alternative causality must be provided (eg, pre-existing condition, underlying disease, intercurrent illness, or concomitant medication).
- **Yes:** There is reasonable possibility that the event may have been caused by the investigational medicinal product.

It should be emphasized that ineffective treatment should not be considered as causally related in the context of adverse event reporting.

The relationship to study procedures (eg, invasive procedures such as venipuncture or biopsy) should be assessed using the following considerations:

- **No:** Evidence exists that the adverse event has an etiology other than the study procedure.
- **Yes:** The adverse event occurred as a result of protocol procedures, (eg., venipuncture)

### **7.2.2. Assessment of Severity**

The severity of AEs will be graded using the National Cancer Institute Common Terminology Criteria for Adverse Events (NCI CTCAE), Version 4.03 in the study manual.

If an NCI CTCAE term is not available for the AE/SAE, the severity will be graded per the General Guidance rules found in the introduction section of the NCI CTCAE , Version 4.03 document.

The distinction between the seriousness and the severity of an AE should be noted. Severe is a measure of intensity; thus, a severe (Grade 3) reaction is not necessarily a serious adverse event (SAE).

### **7.3. Investigator Requirements and Instructions for Reporting Adverse Events and Serious Adverse Events to Gilead**

Requirements for collection prior to study drug initiation:

After informed consent, but prior to initiation of study medication, the following types of events should be reported on the eCRF:

- All SAEs and adverse events related to protocol-mandated procedures

### 7.3.1. Adverse Events

Following initiation of study medication, collect all AEs, regardless of cause or relationship, until 55 days after last administration of GS-5745/placebo or all components of mFOLFOX6, whichever is discontinued later. These must be reported to the eCRF database as instructed.

All AEs should be followed up until resolution or until the adverse event is stable, if possible. Gilead Sciences may request that certain AEs be followed beyond the protocol defined follow-up period.

### 7.3.2. Serious Adverse Events

All SAEs, regardless of cause or relationship, that occurs after the subject first consents to participate in the study (ie, signing the informed consent) and throughout the duration of the study, including the protocol-required post treatment follow-up period, must be reported to the eCRF database and Gilead DSPH as instructed. This also includes any SAEs resulting from protocol-associated procedures performed after informed consent is signed.

Any SAEs and deaths that occur after the post treatment follow-up visit but within 55 days of the last dose of GS-5745/placebo or all components of mFOLFOX6, whichever is discontinued later, regardless of causality, should also be reported.

Investigators are not obligated to actively seek SAEs after the protocol defined follow up period, however, if the investigator learns of any SAEs that occur after study participation has concluded and the event is deemed relevant to the use of study drug, he/she should promptly document and report the event to Gilead DSPH.

- All AEs and SAEs will be recorded in the eCRF database within the timelines outlined in the eCRF completion guideline.
- SAEs will be reported using an electronic SAE (eSAE) system.

#### 7.3.2.1. Electronic Serious Adverse Event (eSAE) Reporting Process

- Site personnel record all SAE data in the eCRF database and from there transmit the SAE information to Gilead DSPH within 24 hours of the investigator's knowledge of the event. Detailed instructions can be found in the eCRF completion guidelines.
- If for any reason it is not possible to record the SAE information electronically, ie, the eCRF database is not functioning, record the SAE on the paper serious adverse event reporting form and submit within 24 hours to:

**Gilead DSPH:**

Fax:

Email:

PPD

PPD

- As soon as it is possible to do so, any SAE reported via paper must be transcribed into the eCRF database according to instructions in the eCRF completion guidelines.
- If an SAE has been reported via a paper form because the eCRF database has been locked, no further action is necessary.
- For fatal or life-threatening events, copies of hospital case reports, autopsy reports, and other documents are also to be submitted by e-mail or fax when requested and applicable. Transmission of such documents should occur without personal subject identification, maintaining the traceability of a document to the subject identifiers.
- Additional information may be requested to ensure the timely completion of accurate safety reports.
- Any medications necessary for treatment of the SAE must be recorded onto the concomitant medication section of the subject's eCRF and the event description section of the SAE form.

#### **7.4. Gilead Reporting Requirements**

Depending on relevant local legislation or regulations, including the applicable US FDA Code of Federal Regulations, the EU Clinical Trials Directive (2001/20/EC) and relevant updates, and other country-specific legislation or regulations, Gilead may be required to expedite to worldwide regulatory agencies reports of SAEs, SADRs, or suspected unexpected serious adverse reactions (SUSARs). In accordance with the EU Clinical Trials Directive (2001/20/EC), Gilead or a specified designee will notify worldwide regulatory agencies and the relevant IEC in concerned Member States of applicable SUSARs as outlined in current regulations.

Assessment of expectedness for SAEs will be determined by Gilead using reference safety information specified in the IB or relevant local label as applicable.

All investigators will receive a safety letter notifying them of relevant SUSAR reports associated with any study drug. The investigator should notify the IRB or IEC of SUSAR reports as soon as is practical, where this is required by local regulatory agencies, and in accordance with the local institutional policy.

#### **7.5. Clinical Laboratory Abnormalities and Other Abnormal Assessments as Adverse Events or Serious Adverse Events**

Laboratory abnormalities are usually not recorded as AEs or SAEs. However, laboratory abnormalities (eg, clinical chemistry, hematology, and urinalysis) that require medical or surgical intervention or lead to interruption or discontinuation of study drug (GS-5745/placebo) or mFOLFOX6 must be recorded as an AE, as well as an SAE, if applicable. In addition, laboratory or other abnormal assessments (eg, electrocardiogram, X-rays, vital signs) that are associated with signs and/or symptoms must be recorded as an AE or SAE if they meet the definition of an AE or SAE as described in Sections 7.1.1 and 7.1.2, respectively. If the laboratory abnormality is part of a syndrome, record the syndrome or diagnosis (ie, anemia) not the laboratory result (ie, decreased hemoglobin).

Severity should be recorded and graded according to the NCI CTCAE (version 4.03).

For AEs associated with laboratory abnormalities, the event should be graded on the basis of the clinical severity in the context of the underlying conditions; this may or may not be in agreement with the grading of the laboratory abnormality.

## **7.6. Toxicity Management**

Treatment-emergent toxicities will be noted by the Investigator and brought to the attention of the Gilead Sciences Medical Monitor or designee. Whether or not considered treatment-related, all subjects experiencing AEs must be monitored periodically until symptoms subside, any abnormal laboratory values have resolved or returned to baseline levels or they are considered irreversible, or until there is a satisfactory explanation for the changes observed.

Grade 3 or 4 clinically significant laboratory abnormalities should be confirmed by repeat testing as soon as practical to do so, and preferably within 3 calendar days after receipt of the original test results. Laboratory abnormalities (eg, thiamine deficiency) identified at screening/baseline and during study participation should be treated at the investigators discretion.

Any questions regarding toxicity management should be directed to the Gilead Sciences Medical Monitor or designee.

## **7.7. Special Situations Reports**

### **7.7.1. Definitions of Special Situations**

Special situation reports include all reports of medication error, abuse, misuse, overdose, reports of adverse events associated with product complaints, and pregnancy reports regardless of an associated AE.

Medication error is any unintentional error in the prescribing, dispensing, or administration of a medicinal product while in the control of the health care provider, subject, or consumer.

Abuse is defined as persistent or sporadic intentional excessive use of a medicinal product by a subject.

Misuse is defined as any intentional and inappropriate use of a medicinal product that is not in accordance with the protocol instructions or the local prescribing information.

An overdose is defined as an accidental or intentional administration of a quantity of a medicinal product given per administration or cumulatively which is above the maximum recommended dose as per protocol or in the product labelling (as it applies to the daily dose of the subject in question). In cases of a discrepancy in drug accountability, overdose will be established only when it is clear that the subject has taken the excess dose(s). Overdose cannot be established when the subject cannot account for the discrepancy except in cases in which the investigator has reason to suspect that the subject has taken the additional dose(s).

Product complaint is defined as complaints arising from potential deviations in the manufacture, packaging, or distribution of the medicinal product.

## **7.7.2. Instructions for Reporting Special Situations**

### **7.7.2.1. Instructions for Reporting Pregnancies**

The investigator should report pregnancies in female study subjects that are identified after initiation of study medication and throughout the study, including the post study drug follow-up period, to Gilead DSPH using the pregnancy report form within 24 hours of becoming aware of the pregnancy.

Refer to the eCRF completion guidelines for full instructions on the mechanism of pregnancy reporting.

The pregnancy itself is not considered an AE nor is an induced elective abortion to terminate a pregnancy without medical reasons.

Any premature termination of pregnancy (eg, a spontaneous abortion, an induced therapeutic abortion due to complications or other medical reasons) must be reported within 24 hours as an SAE. The underlying medical reason for this procedure should be recorded as the AE term.

A spontaneous abortion is always considered to be an SAE and will be reported. Furthermore, any SAE occurring as an adverse pregnancy outcome post study must be reported to Gilead DSPH.

The subject should receive appropriate monitoring and care until the conclusion of the pregnancy. The outcome should be reported to or Gilead DSPH using the pregnancy outcome report form. If the end of the pregnancy occurs after the study has been completed, the outcome should be reported directly to Gilead DSPH.

Pregnancies of female partners of male study subjects exposed to Gilead or other study drugs must also be reported and relevant information should be submitted to Gilead DSPH using the pregnancy and pregnancy outcome forms within 24 hours. Monitoring of the subject should continue until the conclusion of the pregnancy. If the end of the pregnancy occurs after the study has been completed, the outcome should be reported directly to Gilead DSPH.

Gilead DSPH contact information is as follows: Fax: PPD  
Email: PPD

Refer to [Appendix 3](#) for Pregnancy Precautions, Definition for Female of Childbearing Potential, and Contraceptive Requirements.

#### 7.7.2.2. Emergency Unblinding

In the event of a medical emergency where breaking of the blind is being considered by the treating physician, the investigator may break the blind using the IWRS. It is recommended that the Gilead Medical Monitor be contacted before the investigator breaks the blind. Please note that the treatment assignment should not be unblinded if unblinding will not affect the way the subject would be treated. In the event of a medical emergency, where breaking of the blind is required per the medical judgment of the investigator, the Gilead Medical Monitor must be contacted as soon as possible after the unblinding. The unblinding must be clearly justified and explained by a comment in the source documentation, along with the date on which the code was broken and the identity of the person authorizing the unblinding.

Blinding of study treatment is critical to the integrity of this clinical trial and therefore, if a subject's treatment assignment is disclosed to the investigator, the subject will have study treatment discontinued. All subjects will be followed until study completion unless consent to do so is specifically withdrawn by the subject.

Gilead DSPH may independently unblind cases for expedited reporting of SUSARs.

#### 7.7.2.3. Reporting Other Special Situations

All other special situation reports must be reported on the special situations report form and forwarded to Gilead DSPH within 24 hours of the investigator becoming aware of the situation. These reports must consist of situations that involve study IMP and/or Gilead concomitant medications, but do not apply to non-Gilead concomitant medications.

Special situations involving non-Gilead concomitant medications does not need to be reported on the special situations report form; however, for special situations that result in AEs due to a non-Gilead concomitant medication, the AE should be reported on the AE form.

Any inappropriate use of concomitant medications prohibited by this protocol should not be reported as "misuse," but may be more appropriately documented as a protocol deviation.

Refer to the eCRF completion guidelines for full instructions on the mechanism of special situations reporting.

All clinical sequelae in relation to these special situation reports will be reported as AEs or SAEs at the same time using the AE eCRF and/or the SAE report form. Details of the symptoms and signs, clinical management, and outcome will be reported, when available.

## **8. STATISTICAL CONSIDERATIONS**

### **8.1. Analysis Objectives**

#### **8.1.1. Primary Objective**

The primary objective is to compare the efficacy of GS-5745 versus placebo in combination with mFOLFOX6 as measured by OS.

#### **8.1.2. Secondary Objectives**

The secondary objectives are:

- To compare the efficacy of GS-5745 versus placebo in combination with mFOLFOX6 as measured by PFS
- To compare the efficacy of GS-5745 versus placebo in combination with mFOLFOX6 as measured by ORR per RECIST v1.1
- To compare the safety profile of GS-5745 versus placebo in combination with mFOLFOX6

#### **8.1.3. Exploratory Objectives**

### **8.2. Analysis Endpoints**

#### **8.2.1. Primary Endpoint**

The primary endpoint of the study is OS as defined in Section [2.4](#).

#### **8.2.2. Secondary and Exploratory Endpoints**

The secondary and exploratory endpoints of the study are defined in Section [2.5](#).

### **8.3. Analysis Conventions**

#### **8.3.1. Analysis Sets**

##### **8.3.1.1. Intent-to-Treat (ITT) Analysis Set**

The ITT analysis set includes data from all randomized subjects. Study drug assignment will be designated according to randomization.

This analysis set will be used in the analyses of subject characteristics, OS, PFS, ORR and DCR. The analysis of OS based on the ITT analysis set will be considered the primary analysis of the study.

Subjects in the ITT analysis set who do not have sufficient baseline or on-study tumor status information to be adequately assessed for response status (ie, those with best overall responses of NE or ND) will be included in the denominators in calculations of response rates and disease control rates.

##### **8.3.1.2. Safety Analysis Set**

The safety analysis set will include data from all subjects who receive  $\geq 1$  dose of study treatment, with treatment assignments designated according to the actual treatment received.

This analysis set will be used in the analysis of safety variables as well as study treatment administration. All data collected up to the last dose of GS-5745/placebo or mFOLFOX6 or 5-FU and LV, whichever is later, plus 55 days will be included in the safety summaries.

##### **8.3.1.3. Pharmacodynamic and Pharmacokinetic (PK) Analysis Sets**

The pharmacodynamics and PK analysis sets will include data from subjects in the safety analysis set who have the necessary baseline and on-study measurements to provide interpretable results for the specific parameters of interest.

### **8.4. Data Handling Conventions**

#### **8.4.1. General Methods**

By-subject listings will be created for important variables from each eCRF module.

Summary tables for continuous variables will contain the following statistics:

N (number in analysis set), n (number with data), mean, standard deviation (std), 95% confidence intervals (CIs) on the mean, median, minimum, and maximum. Summary tables for categorical variables will include: N, n, percentage, and 95% CIs on the percentage. Unless otherwise indicated, 95% CIs for binary variables will be calculated using the binomial distribution (exact method) and will be 2-sided. Data will be described and summarized by relevant treatment arm, analysis set, and time point. As appropriate, changes from baseline to

each subsequent time point will be described and summarized by treatment arm. Similarly, as appropriate, the best change from baseline during the study will also be described and summarized by treatment arm. Graphical techniques (eg, waterfall plots, Kaplan-Meier curves, etc.) may be used when such methods are appropriate and informative.

The baseline value used in each analysis will be the last (most recent) pre-treatment value.

Subjects with discrepancies between the stratification factor values at randomization and the actual values as documented on data review will be categorized in the analyses according to the actual values. In the situation that there is insufficient information in a stratum (ie, if there are < 6 subjects or there are no events in a stratum), that stratum will be pooled with the smallest adjacent stratum for stratified analyses; the smallest stratum is defined as that stratum having the fewest number of subjects or the fewest number of events in case the former is a tie and the adjacent stratum is defined as a stratum having 2 factors of the 3 at the same level. Data from all sites will be pooled for all analyses. Analyses will be based upon the observed data unless methods for handling missing data are specified. If there is a significant degree of non-normality, analyses may be performed on log-transformed data or nonparametric tests may be applied, as appropriate.

Unless otherwise specified, all analyses will be 1-sided at the 0.025 level of significance.

The following censoring conventions will be applied to tumor control endpoints:

- OS: Data from surviving subjects will be censored at the last time that the subject was known to be alive.
- PFS: Data from surviving, non-progressing subjects will be censored at the earliest of the time of initiation of antitumor treatment other than the study treatment or the last time that lack of definitive progression was objectively documented. Data from subjects who have disease progression or die after  $\geq 2$  consecutive missing tumor assessments will be censored at the last time prior to the missing assessments that lack of definitive disease progression was objectively documented.
- DOR: Data from surviving, non-progressing subjects will be censored at the earliest of the time of initiation of antitumor treatment other than the study treatment or the last time that lack of definitive disease progression was objectively documented. Data from subjects who have disease progression or die after  $\geq 2$  consecutive missing tumor assessments will be censored at the last time prior to the missing assessments that lack of definitive disease progression was objectively documented.

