### 6.2.9. Disease and Response Assessment

#### 6.2.9.1. Tumor Imaging

Either contrast-enhanced CT or gadolinium-enhanced MRI of the chest, abdomen, and pelvis will be performed at screening, every 8 weeks during the study (starting from Cycle 1 Day 1) and at the EOS visit if one has not been performed within the last 8 weeks. Tumor burden will be evaluated solely based on radiographic imaging per RECIST v 1.1. Chest x-ray, ultrasound, endoscopy, laparoscopy, positron-emission tomography, radionuclide scans, or tumor markers will not be considered for response assessment.

For radiographic evaluations, the same method of assessment and the same technique (eg, scan type, scanner, subject position, dose of contrast, injection/scan interval) should be used to characterize each identified and reported lesion at baseline and during study treatment and follow-up.

Scans taken as part of standard medical practice up to 42 days prior to randomization can be used for Screening as long as they meet all study requirements. During the treatment phase, scans may be performed at time points other than every 8 weeks as clinically indicated to assess tumor progression.

For subjects who stop study treatment in the absence of disease progression (eg, experienced unexpected toxicity), scans should continue to be collected approximately every 8 weeks until disease progression or initiation of systemic anti-tumor therapy other than the study treatment, whichever is earlier.

All relevant clinical and radiographic information required to make each assessment must be made available for source verification and submission to a central reader. Scans will be transferred to a central reader for collection and future analysis. Disease progression will be determined by the investigator or qualified designee.

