## **6.2. Secondary Efficacy Endpoint**

### **6.2.1. Definition of the Secondary Efficacy Endpoints**

#### **6.2.1.1. Progression-Free Survival**

Progression-free survival is defined as the time interval from the date of randomization to the earlier of the first documentation of definitive disease progression or death from any cause. All scans, whether scheduled or unscheduled, will be considered.

The date of definitive progression will be the time point at which progression is first identified by relevant radiographic imaging data. Data will be censored on the date of last adequate tumor assessment for subjects (including assessments with a not evaluable [NE] outcome):

- who do not have disease progression or die before study discontinuation, or
- who start new anticancer therapy prior to documented disease progression or death, or
- who have  $\geq 2$  consecutive missing tumor assessments before disease progression or death

If a subject does not have a baseline tumor assessment, then PFS will be censored at Study Day 1, regardless of whether or not definitive progression or death has been observed.

PFS in months will be calculated by  $(\text{date of event/censoring} - \text{date of randomization} + 1) / 30.4375$ .

When imaging examinations for one visit are conducted on various dates, the following rules apply for the calculation of the assessment date:

- The response date will be the last date associated with that particular imaging time point.
- The progression date will be the first date associated with that particular imaging time point.

When the date of initiation of anticancer therapy other than the study treatment is incomplete or missing, the following algorithm will be followed:

- If the day is missing but the month and year are available, then the imputed day will be the last day of the month.
- If day and month are missing but year is available, then the imputed day and month will be 01Jan or the last day of the month for the last adequate disease assessment if they have the same year, whichever is later.

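### As written, the two-missed-scans PFS rule lets an earlier gap void a later, well-dated event, and the protocol and SAP censor that subject at different dates

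*Protocol*

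**What the plan says.** Protocol 8.4.1 states the PFS rule as "Data from subjects who have disease progression or die after" two or more "consecutive missing tumor assessments will be censored at the last time prior to the missing assessments" at which absence of definitive progression had been objectively documented. The duration-of-response rule there has the same wording.

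SAP 6.2.1.1 has one censoring date for three situations: "Data will be censored on the date of last adequate tumor assessment for subjects (including assessments with a not evaluable [NE] outcome"). The third situation is two or more "consecutive missing tumor assessments before disease progression or death". The same section adds that "All scans, whether scheduled or unscheduled, will be considered".

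Protocol 6.2.9.1 schedules imaging every 8 weeks. For subjects who stop treatment without progression, "scans should continue to be collected approximately every 8 weeks until disease progression" or start of another systemic anti-tumor therapy. Scans after a gap are therefore expected data.

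SAP 2.4, on changes from the protocol analysis, lists only the PD-L1 subgroups.

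**The concern.** A missed-scan rule is there for events whose date is uncertain because nobody looked for a long time. A gap followed by scans showing no progression leaves no such uncertainty: the later event is bracketed by ordinary 8-week scans. The linking words are *after* in the protocol and *before* in the SAP. Neither demands adjacency, and neither restores a subject whose scanning resumed. Taken as written, both discard a sound event.

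They also date the censoring differently for that subject. The protocol ties the date to the start of the gap. The SAP does not, and it accepts a scan that was not evaluable, which cannot document absence of progression.

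PFS is the first secondary endpoint in the gatekeeping order (protocol 8.5.3), tested at one-sided 0.016, and ORR can be tested only if PFS succeeds. Two programmers working from the two documents could produce different PFS data sets for a test with alpha control.

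**Working it through.** **1. The plan's own figure.** Protocol 8.11 and SAP 1.3 give HR 0.7, one-sided alpha 0.016, 322 events and 85% power; allocation is 1:1. Using the Schoenfeld formula:

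power = Φ(√d/2 × |ln HR| − z) = Φ(√322/2 × 0.3567 − 2.144) = Φ(3.200 − 2.144) = Φ(1.056) = 85.4%.

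This reproduces the stated 85%. Exponential PFS with medians 9 and 9/0.7 = 12.86 months, 18 months of uniform accrual, 18 months minimum follow-up and 10% annual dropout gives 321 to 322 expected events, depending on how the dropout rate is converted. That agrees with 322.

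**2. One subject under both texts.** Suppose scans at Weeks 8 and 16 show no progression, Weeks 24 and 32 are missed, Weeks 40 and 48 show no progression, and Week 56 shows progression. Study day is 7 × week + 1 (SAP Table 3-3). Months are day/30.4375 (SAP 6.2.1.1), taking randomization as Day 1.

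| Rule | PFS record | Time |
|---|---|---|
| Protocol, literal | censored at Week 16, day 113 | 3.71 months |
| SAP, literal | censored at Week 48, day 337 | 11.07 months |
| Rule limited to adjacent gaps | event at Week 56, day 393 | 12.91 months |

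The two censoring dates differ by 32 weeks (11.07 − 3.71 = 7.36 months), and neither document counts the progression. The SAP date assumes that the last adequate assessment means the last one before the event. The SAP does not say so, and the Week 56 scan is itself an adequate assessment.

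**3. How often.** The documents give no missed-scan rate, so this step rests on assumptions: each scan is missed independently with the probability shown, 15% of events are deaths, and progression is dated at the first attended scan after it occurs, because SAP 6.2.1.1 dates it when first identified on imaging. Other inputs are as in step 1, with scans every 56 days. The simulation used 50,000 subjects, about 36,600 of them with events. *Earlier gap only* is any gap minus direct gap. Power is recomputed as in step 1 after removing the earlier-gap-only events alone.

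| Scans missed | Direct gap | Any gap | Earlier gap only | Of 322 events | Power |
|---|---|---|---|---|---|
| 2% | 0.07% | 0.16% | 0.09% | 0.3 | 85.4% |
| 5% | 0.59% | 1.28% | 0.69% | 2.2 | 85.2% |
| 10% | 1.98% | 4.50% | 2.52% | 8.1 | 84.5% |
| 15% | 4.39% | 9.48% | 5.09% | 16 | 83.5% |

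The ratio of earlier-only to direct gaps is 0.69/0.59 = 1.2 at 5% missed and 2.52/1.98 = 1.3 at 10%. With 30% deaths the earlier-only shares barely change (0.69% and 2.49%) and the ratio is about 1.4.

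Direct-gap events are censored under either reading. Counting both kinds, the literal rule at 10% missed leaves power at 83.7%, against 84.7% with the rule limited to adjacent gaps.

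At 5% to 15% missed, the median difference between the protocol and SAP censoring dates in affected subjects was about 9 months.

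**The case against.** An event after a gap can naturally be read as the event that follows it, and the protocol's censoring point fits that reading: it is the last known status before an uncertain event. On that reading, if the last pre-gap scan was evaluable, the protocol and SAP dates normally coincide. This stands in part. The narrower rule may well have been intended, and the date conflict is confined mainly to subjects who resume scanning and to those whose last pre-gap scan was not evaluable. But adjacency is not written in either document.

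The effect on power is small and PFS is tested only if OS succeeds. Both points stand; the OS conclusion is untouched.

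The trial is double-blind and both arms follow one imaging calendar, so a difference in missed scans between arms is not to be presumed. That also stands.

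The contiguous windows in SAP Table 3-3 would make true gaps rarer, since a late or unscheduled scan would fill a window. The SAP does not tie the word *missing* to those windows. The list of PFS sensitivity analyses under SAP 6.2.4 is not visible in the public text, and the SAP's exploratory endpoint definitions are redacted. No absence is held against either.

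A reader might infer that the rule destroys several sound events for each one it is meant to catch. Dating progression at its true time, whether or not the next scan took place, gives 0.2% direct against 0.7% earlier-only at 5% missed, and 0.7% against 2.6% at 10%, or about 3.7 to 1. The SAP does not date progression that way. A missed scan delays detection, and that delay creates most of the direct gaps, so the ratio falls to about 1.2.

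**Conclusion.** The point holds on the text of both documents. The missed-scan rule is not limited to an event that directly follows the gap. For a subject who resumes scanning, the two documents give different PFS times and neither counts the event.

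If 5% to 10% of scans are missed independently, the literal rule voids about 0.7% to 2.5% of PFS events (2 to 8 of 322) only because of an earlier gap. That is roughly as many as the rule is meant to catch. Taken alone, the loss lowers PFS power from 85.4% to no lower than about 84.5%; clustered non-attendance or a higher miss rate would raise it.

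The documents do not support reading this as a material loss of power, as a conflict for every gap, or as demonstrated bias. Bias would require missed scans to differ between arms or to relate to prognosis. The reason to act is that an alpha-controlled endpoint should have one definition that can be reproduced. The change should be made, but it does not threaten the trial's main conclusion.

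**What to change.** Put one rule in protocol 8.4.1 (PFS and duration of response) and SAP 6.2.1.1, for example:

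> Progression or death that occurs immediately after two or more consecutive missed scheduled assessments, with no adequate assessment in between, is censored at the last adequate, evaluable assessment without progression before that gap.

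Use that single date in both documents, and define a missed assessment by the windows in SAP Table 3-3. If the protocol is not amended, declare the difference in SAP 2.4. The cost is one sentence in each document and minor programming, with no new data collection. It should be settled before unblinding, so that the choice cannot be linked to the result.
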